6.3.3 Response Criteria for CTCL

Global Response (GR) score (**APPENDIX C**) will be used for assessing response in patients with CTCL (53). GR score incorporates separate responses in each component of the TNBM staging (i.e., skin, nodes, viscera and blood; **APPENDIX C**). No patient with a global OR should have less than a PR in the skin.

The mSWAT (11) is an instrument utilized to track the skin tumor burden in MF/SS. It measures the percentage total body-surface area (TBSA, %) involvement separately for patches, plaques, and tumors within 12 body regions using the patient's palm and fingers representing 1% of TBSA. Patients with erythroderma are assessed for percentage of TBSA involved with patches and/or plaques. The percentage of TBSA for each lesion type is multiplied by a number (patch = 1, plaque = 2; tumor = 4) and summed to derive the mSWAT score. The mSWAT for each patient will be determined by the same individual at all study visits.

A complete response (CR) requires 100% clearing of skin disease and a partial response (PR) requires $\geq 50\%$ reduction in the mSWAT score compared with baseline. CR/PR requires confirmation by repeat assessment after ≥ 4 weeks. Stable disease is defined as less than 50% reduction to less than 25% increase in the mSWAT score compared with baseline. PD is defined as $\geq 25\%$ increase in the mSWAT score from baseline or $\geq 50\%$ increase in the sum of the products of the greatest diameters of pathologically positive lymph nodes compared with baseline.

Time to response is the time from the first treatment dose until the patient first meets the criteria for a 50% decrease in the GR score. The duration of response (DOR) is the time from first CR/PR until the GR score is increased from nadir to more than 50% of the difference between the baseline and nadir scores. Time to progression (TTP) is the time from start of treatment until PD. If patients goes off treatment for any purpose, this date is used for determination of TTP and/or DOR.

As “skin flares” have been described in patients with SS receiving the anti-PD-1 antibody Pembrolizumab (18), patients with SS whose only sign of PD is an increase in mSWAT score (i.e., who have normal/decreasing number of circulating Sézary cells) will continue treatment and be re-evaluated in 2-4 weeks to confirm disease progression. Patients whose PD is not confirmed on re-evaluation will be noted to have had a skin flare

Table 15: Calculating mSWAT Score

Body Region	% BSA in Body Region	Assessment of Involvement in Patient's Skin		
		Patch ¹	Plaque ²	Tumor ³
Head	7			
Neck	2			
Anterior trunk	13			
Arms	8			
Forearms	6			
Hands	5			
Posterior trunk	13			
Buttocks	5			
Thighs	19			
Legs	14			
Feet	7			
Groin	1			
Subtotal of lesion BSA				

Weighing factor		x1	x2	x4
Subtotal lesion BSA x weighing factor				

NOTE: mSWAT score equals summation of each column line.

Abbreviations: BSA, body surface area; mSWAT, modified Severity Weighted Assessment Tool.

¹ Any size lesion without induration or significant elevation above the surrounding uninvolved skin; poikiloderma may be present

² Any size lesion that is elevated or indurated; crusting, ulceration, or poikiloderma may be present.

³ Any solid or nodular lesion \geq 1cm in diameter with evidence of deep infiltration in the skin and/or vertical growth.

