6.3.5 Best Overall Response

The best overall response is the best response recorded from the start of the treatment until disease progression/recurrence (taking as reference for progressive disease the smallest measurements recorded since the treatment started). The patient's best response assignment will depend on the achievement of both measurement and confirmation criteria.

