16.2 APPENDIX B: ASSAY FOR ADCC

- Peripheral blood mononuclear cells (PBMCs) should be isolated by Ficoll-High-Paque Density Gradient Centrifugation.
- The viable cells should be viably frozen and stored in liquid nitrogen.
- The ADCC assay will be performed on the same occasion for all samples of a given patient.
- Vials of frozen cells will be thawed using standard procedures 18 hours before the assay in accordance with our experience with normal donors.
- 1.5 million of patient's PBMCs obtained before and on day 15 following IL-15 injection will be tested in aliquots as follows:
 - Tested alone
 - Tested with untreated PD-L1-expressing Raji cells and with PD-L1-expressing Raji cells coated with avelumab for 5 hours.
 - In addition, we may utilize an ATL cell line in addition to Raji cells. These cell populations will be stained with CD107, CD3, CD56 and CD94.

16.3 APPENDIX C: GLOBAL RESPONSE SCORE AND DEFINITIONS OF RESPONSE IN SKIN, LYMPH NODES, VISCERA, AND BLOOD

Global Response Score					
Global Score	Definition	Skin	Nodes	Blood	Viscera
CR	Complete disappearance of all clinical evidence of disease	CR	All categories have CR/NI		
PR	Regression of measurable disease	CR	All categories do not have a CR/NI and no category has a PD		
		PR	No category has a PD and if any category involved at baseline at least one has a CR or PR		
SD	Failure to attain CR, PR, or PD representative of all disease	PR	No category has a PD and if any category involved at baseline, no CR or PR in any		
		SD	CR/NI, PR, SD in any category and no category has a PD		
PD	Progressive disease	PD in any category			
Relapse	Recurrence of disease in prior CR	Relapse in any category			

Abbreviations: CR, complete response; NI, noninvolved; PR, partial response; PD, progressive disease; SD, stable disease.

Response in Skin	
Response	Definition
Complete response	100% clearance of skin lesions
Partial response	50%-99% clearance of skin disease from baseline without new tumors (T3) in patients with T1, T2 or T4 only skin disease
Stable disease	<25% increase to <50% clearance in skin disease from baseline without new tumors (T3) in patients with T1, T2, or T4 only skin disease
Progressive disease	≥25% increase in skin disease from baseline or New tumors (T3) in patients with T1, T2, or T4 only skin disease or Loss of response: in those with complete or partial response, increase of skin score of greater than the sum of nadir plus 50% baseline score

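### CTCL progression is defined differently in Section 6.3.3, Appendix C and Sections 6.3.5/6.3.6, and the protocol does not say which definition the endpoints use

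*Combined protocol and SAP*

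**What the plan says.** Section 6.3.1 names the Global Response Score and mSWAT for CTCL. Section 6.3.3 opens by adopting the Global Response of Appendix C and explains that the "GR score incorporates separate responses in each component of the TNBM staging", that is skin, nodes, viscera and blood.

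The same section then gives its own categories. "PD is defined as $\geq 25\%$ increase in the mSWAT score from baseline", or at least a 50% "increase in the sum of the products of the greatest diameters of pathologically positive lymph nodes compared with baseline". Stable disease is any mSWAT between a reduction short of 50% and a rise short of 25%, again against baseline. Blood, viscera, new tumors, new nodes and loss of response do not appear in these sentences.

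In Appendix C, global progression is "PD in any category". The skin table adds new tumors (in T1, T2 or T4-only disease) and, for former responders, an "increase of skin score of greater than the sum of nadir plus 50% baseline score". The node, viscera and blood tables each have their own progression and loss-of-response criteria.

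Sections 6.3.5 and 6.3.6 set a general reference point, "taking as reference for progressive disease the smallest measurements recorded since the treatment started". Section 6.3.3 has a separate rule for duration of response (DOR), which runs "until the GR score is increased from nadir to more than 50% of the difference between the baseline and nadir scores".

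**The concern.** Three texts answer the question of when a CTCL patient has progressed, and they need not give the same date or even the same category.

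Progression feeds best response, DOR, time to progression (TTP), PFS and EFS. PFS, EFS and DOR are secondary endpoints in Section 10.1, and Section 10.4.7 reports them separately for MF/SS. Progression also defines rapid progression (6.3.4). Once confirmed, it moves the patient to survival-only contact (3.5.4), so later disease assessments may not exist to correct a date.

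The blood compartment matters here because criterion 2.1.1.4 admits patients on the strength of a clonal T-cell population in blood alone.

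**Working it through.** The plan gives no figure to reproduce. The check compares the texts and works out their thresholds for an illustrative patient.

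**Assumptions.** Baseline mSWAT B = 100, chosen for scale, and a nadir N that qualifies as a partial response (N of 50 or less). The Global Response in Appendix C is a category (CR, PR, SD, PD, relapse), so a percentage change in it cannot be computed. mSWAT is used in its place for the DOR rule.

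**Formulas.**
- 6.3.3 progression: score ≥ 1.25 × B
- Appendix C skin loss of response: score > N + 0.5 × B
- 6.3.3 end of DOR: score > N + 0.5 × (B − N), or read literally, score > 0.5 × (B − N)

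| Nadir N | 6.3.3 progression | Appendix C loss of response | 6.3.3 end of DOR | 6.3.3 end of DOR, literal |
|---|---|---|---|---|
| 5 | ≥ 125 | > 55 | > 52.5 | > 47.5 |
| 10 | ≥ 125 | > 60 | > 55 | > 45 |
| 25 | ≥ 125 | > 75 | > 62.5 | > 37.5 |
| 50 | ≥ 125 | > 100 | > 75 | > 25 |

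For N = 10: 1.25 × 100 = 125; 10 + 50 = 60; 10 + 0.5 × 90 = 55; 0.5 × 90 = 45. At N = 50 the literal DOR threshold of 25 lies below the nadir itself, so that reading cannot work for shallow responses.

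**Opposite categories.** With N = 10 and a current score of 70, the reduction from baseline is 30%. Section 6.3.3 calls this stable disease. Appendix C calls it progression, since 70 > 60. This takes the Appendix C threshold as a score level and lets the loss-of-response criterion override its stable-disease row. If the threshold meant a rise from nadir, it would be 10 + 60 = 70. A score of exactly 70 would then just miss, but scores above 70 and below 125 would still be classified differently.

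**Nodes.** With a baseline sum of products of 100 and a nadir of 25, 6.3.3 needs at least 1.5 × 100 = 150. Appendix C loss of response needs more than 1.5 × 25 = 37.5.

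**Blood and viscera.** The 6.3.3 sentence has no criterion. Appendix C has one for each. In blood it is B0 to B2, or more than a 50% rise with at least 5,000 neoplastic cells/µL, from baseline or, in partial responders who began at B2, from nadir.

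**Sections 6.3.5/6.3.6 against Appendix C.** Appendix C keeps baseline as the reference for the 25% skin and 50% nodal increases and uses nadir only for loss of response. Sections 6.3.5 and 6.3.6 use the smallest measurement for all progression. Naming Appendix C without limiting that wording would leave this conflict open.

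**The case against.** A reader might infer that patients who lose a deep response, or who progress in blood or viscera, are not counted as progressing at all. The documents do not support that. Sections 6.3.1 and 6.3.3 both adopt the Global Response, under which such patients progress once they meet the Appendix C criteria. They are missed only if one sentence overrides the adopted instrument, and nothing says it does. The two criteria in that sentence also appear in Appendix C. The skin-flare rule in 6.3.3 treats circulating Sézary cells as a possible sign of progression.

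The effect on endpoints is also limited:
- PFS and EFS count relapse separately (6.3.7, 6.3.9), so recurrence after complete response can be an event whatever the progression sentence says.
- Section 6.3.3 ends TTP and DOR at the off-treatment date, and its DOR rule is already nadir-based.
- A later stable-disease label does not erase a confirmed earlier response.
- Rising Sézary counts alone are not progression under Appendix C either.
- These are secondary, descriptive endpoints in at most 30 patients.

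A reader might also apply the 25% rule to the nadir and quote a threshold of 1.25 × 10 = 12.5. Section 6.3.5 gives no percentage, so that figure belongs to no section.

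These points narrow the finding but do not remove it. The stable-disease sentence gives a different category from Appendix C for the same score, and no order of precedence is stated.

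**Conclusion.** The protocol holds competing CTCL progression definitions without precedence, plus a DOR rule that matches neither Appendix C nor Section 6.3.6 and cannot be computed on a categorical score. In the illustration (baseline 100, nadir 10), scores above 60 and below 125 are progression under Appendix C but not under the 6.3.3 sentence.

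Read literally, that sentence can lengthen PFS and EFS in MF/SS. This applies mainly to partial responders who lose response, and to non-responders whose progression is by new tumors, blood or viscera. The trial-level effect cannot be quantified because the number of CTCL patients is not stated. The thresholds rest on the assumed baseline and nadirs and on mSWAT standing in for the Global Response. The primary endpoints of maximum tolerated dose and adverse events are not at issue. The point should be settled before the secondary endpoints are derived.

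**What to change.** For endpoint derivation:
- State one CTCL definition of progression and relapse for best response, DOR, TTP, PFS and EFS. Appendix C is the natural choice, since 6.3.1 and 6.3.3 already adopt it.
- Delete the stable-disease and progression sentences in 6.3.3, or label them as skin and node component criteria.
- Replace the 6.3.3 time-to-response and DOR sentences with wording consistent with Appendix C and 6.3.6.
- State that the smallest-measurement reference in 6.3.5 and 6.3.6 applies to CTCL only through the Appendix C loss-of-response criteria.

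Progression also appears in 3.8.1 and in the skin-flare rule. The sponsor must reconcile those passages with the definition; which rule governs stopping treatment is the sponsor's decision.

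The cost is mainly wording. Reported PFS and EFS may become slightly shorter. Study calendar note 15 allows, but does not require, blood flow cytometry at disease evaluation in CTCL, so the sponsor should check that blood will be assessed often enough to support the chosen definition.

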2.4 BASELINE EVALUATION

The following should be performed within 28 days prior to the first dose of rhIL-15 unless otherwise noted; tests performed as part of screening do not need to be repeated if they were performed within the specified window prior to initiating treatment.

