3.5.3 Follow-Up Visits- Prior to Disease Progression

Patients who complete trial treatment without evidence of disease progression will move into the Follow-up Phase and may be assessed every 60 days (\pm 7 days) for 6 months; then every 90 days (\pm 14 days) for 2 years; then every six months (\pm 28 days) for 2 years, then annually (\pm 6 weeks) after finishing treatment by radiologic imaging or other clinical assessments to monitor disease status. Imaging assessment will be performed at each scheduled post-treatment follow-up visit for up to 3 years. Every effort should be made to collect information regarding disease status until the start of new anti-neoplastic therapy, disease progression, death, or end of the study. If the patient cannot return to the Clinical Center for any of these visits, a request will be made to have a local physician or laboratory collect a CBC with differential and send the results. If this is not possible, patients may be assessed by telephone or email for symptoms.

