3.6 STUDY CALENDAR

Procedure	Screening	Baseline		Study Cycles								Disease Evaluations	End of Treatment and Disease Progression	Post-Treatment Follow-Up		
				C1				C2-6						Safety ¹	Follow-Up (Prior to PD)	Survival (Post-PD)
Scheduling Window (Days):	-28 to -1 ²	-14 ³		5 (-1)	8 (-3)	9	22 (-3)	1 (-3)	8 (-3)	22 (-3)	Every 8 weeks ⁴	Treatment discon/PD ⁵	Day 30 (±7)	Every 60 or 90 days ⁶	Every 3 months ⁷	
Confirmation of Diagnosis ⁸	X															
Physical Exam and ECOG PS ⁹	X	X			X		X	X	X	X		X	X	X		
CBC with Differential	X	X	X		X		X	X	X	X		X	X	X		
Reticulocyte Count	X	X	X		X		X	X	X	X		X	X	X		
Chemistry Panels ¹⁰	X	X	X		X		X	X	X	X		X	X	X		
LDH, Serum Lipase and Amylase	X	X	X		X		X	X	X	X		X	X	X		
Uric Acid, Total Protein		X	X		X		X	X	X	X						
PT/INR and aPTT	X	X	X				X					X	X	X		
Thyroid Function (TSH, reflex free T4)	X	X	X				X					X	X	X		
Urinalysis	X	X	X				X					X				
Pregnancy Test (urine/serum; WOCCBP)	X	X	X													
Hepatitis B and C, HIV Antibody, HTLV-1/2	X															
HLA typing (A, B, C, DR, DQ)		X	X													
Anti-nuclear antibody (ANA), rheumatoid factor (RF) and anti-thyroid antibody	X	X														
Clonal T-cell receptor rearrangement by PCR	X															
Iron panels, Folate, and B12, C-reactive Protein, IL-2R		X	X													
Creatine phosphokinase (CPK), troponin	X	X	X									X		X		

Abbreviated Title: IL-15 and Avelumab in R/R T-cell NHL

Version Date: 09/23/2021

Procedure	Screening	Baseline		Study Cycles								Disease Evaluations	End of Treatment and Disease Progression	Post-Treatment Follow-Up		
				C1				C2-6						Safety ¹	Follow-Up (Prior to PD)	Survival (Post-PD)
Scheduling Window (Days):	-28 to -1 ²	-14 ³		5 (-1)	8 (-3)	9	22 (-3)	1 (-3)	8 (-3)	22 (-3)	Every 8 weeks ⁴	Treatment discon/PD ⁵	Day 30 (+7)	Every 60 or 90 days ⁶	Every 3 months ⁷	
Pulmonary function tests (PFTs) ¹¹	X															
T, B, NK cell subsets		X			X			X	X			X	X	X		
Imaging studies ¹²	X	X										X	X		X	
MRI, Lumbar Puncture ¹³		X										X	X		X	
Bone Marrow Aspiration/Biopsy ¹⁴		X										X	X			
Flow Cytometry ¹⁵		X										X	X	X	X	
Clinical photography and dermatology assessment/ global score ¹⁶		X										X	X		X	
Radiologic Evaluation/ tumor measurement ¹⁷		X										X	X		X	
EKG, TTE	X															
Symptoms/Adverse Events Assessment, Concomitant Medication Review	X	X						X				X	X	X	X	
Research Blood/Tissue Samples ¹⁸		X	X	X	X	X	X	X	X		X	X	X	X		
Survival Status																X

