NOTE: Any other tests should be performed as clinically indicated. See Section 3.2 for drug administration information. See Section 5 for information on research blood samples/correlative studies to be collected.

¹ 30 days (± 7) following last dose, and 90 days ($+14$) after last dose of avelumab (via clinic or phone). If initiating new anti-cancer therapy within 30 days after last dose of avelumab, 30-day safety follow-up visit must occur before first dose of new therapy.

² Screening and Baseline evaluations should be performed within 28 days prior to enrollment and dosing, respectively, unless otherwise noted and with the following exceptions: Confirmation of diagnosis (no time limit); HIV antibody, HTLV-1/2 serologies, Hepatitis B surface antigen and Hepatitis C antibody, EKG, and bone marrow aspiration/biopsy (all within 3 months) **NOTE:** Any screening tests performed within the specified time frame for baseline do not need to be repeated.

³ Within 14 days prior to dosing on C1D1, with the following exceptions: Pregnancy test (within 7 days of dosing; must be negative).

⁴ ± 4 days, from date of prior assessment. Confirmatory scans should also be obtained 4 weeks following initial documentation of objective response. After completion of treatment, imaging assessment will be performed at each scheduled post-treatment follow-up visit for up to 3 years.

⁵ To be done at end of treatment (30 days after last dose of study treatment; may be combined with 30 day safety follow-up, if timing coincides). If subject to initiate new anti-cancer therapy assessments should occur before the first dose of the new therapy.

⁶ Follow-up to occur about every 60 days (± 7 days) for first 6 months, every 90 days (± 14 days) for 2 years, then every 6 months (± 28 days) for another 2 years and then annually (± 6 weeks) until disease progression or initiation of new anti-cancer therapy. After completion of treatment, imaging assessment will be performed at each scheduled post-treatment follow-up visit for up to 3 years.

⁷ After disease progression or initiation of new anti-cancer therapy, contact for survival about every 3 to 6 months (± 4 weeks).

⁸ Pathologic review/confirmation of diagnosis by Laboratory of Pathology, NCI (no time limit). If archival sample is not available, a fresh tumor biopsy and/or peripheral blood sample will be obtained.

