3.8.1 Criteria for removal from protocol therapy

Patients who meet the following criteria should be discontinued from protocol therapy:

- Completion of protocol therapy (i.e., up to 6 cycles)
- Confirmed disease progression
- Intercurrent illness that prevents further administration of treatment
- Unacceptable toxicities as listed in Section [3.1.1](#) or those toxicities listed in Section [3.3](#) that require treatment to be stopped
- More than 6 weeks has elapsed since the patient received protocol therapy
- Subject's request to withdraw from protocol therapy
- Investigator's decision to withdraw the patient
- Subject's non-compliance with trial treatment or procedure requirements that requires removal in the opinion of the PI
- Pregnancy
- The drug manufacturer can no longer prove the study agent
- Study is cancelled for any reason

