6.3.6 Duration of Response

The duration of response (DOR) is measured from the time measurement criteria are met for CR or PR (whichever is recorded first) until the first date that recurrent or progressive disease is objectively documented (taking as reference for progressive disease the smallest measurements recorded since the treatment started), death, or, in the absence of PD, date of last assessment.

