10.4.7 Sub-Group Analyses

All secondary endpoints will be analyzed and reported separately according to the presenting diagnosis (PTCL-NOS, MF/SS, ALCL, or Other) and baseline PD-L1 expression (<1%, $\geq 1\%$, $\geq 5\%$, $\geq 10\%$, $\geq 50\%$).

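### Section 6.3.3 ends CTCL duration of response at the off-treatment date, which caps it at treatment length and conflicts with section 6.3.6

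*Combined protocol and SAP*

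**What the plan says.** Section 6.3.3 (CTCL) starts DOR at first CR or PR. It ends DOR when the global response score rises from nadir past a threshold based on half the baseline-to-nadir difference. It then adds: "If patients goes off treatment for any purpose, this date is used for determination of TTP and/or DOR".

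Section 6.3.6, which is not limited to any diagnosis, runs DOR "until the first date that recurrent or progressive disease is objectively documented", or to death, or to the last assessment if there is no progression. It does not mention end of treatment.

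Sections 3.1 and 3.2 cap treatment at six 28-day cycles. Among the criteria for leaving therapy, section 3.8.1 lists "Completion of protocol therapy (i.e., up to 6 cycles".

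Patients off treatment without progression stay under disease follow-up. Section 3.5.3 states: "Imaging assessment will be performed at each scheduled post-treatment follow-up visit for up to 3 years". The Study Calendar (3.6) also has a post-treatment entry for "Clinical photography and dermatology assessment/ global score".

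DOR is a listed secondary endpoint (10.1), estimated by Kaplan-Meier (10.4.3). Section 10.4.7 adds: "All secondary endpoints will be analyzed and reported separately according to the presenting diagnosis (PTCL-NOS, MF/SS, ALCL, or Other". The same section also splits every secondary endpoint by baseline PD-L1 level.

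**The concern.** Because the rule applies whatever the reason for stopping, it covers planned completion. DOR in a lasting CTCL response then measures the length of the treatment course.

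Section 6.3.3 does not say how the date enters the Kaplan-Meier analysis, and both readings do harm:
- **As an event**, completing therapy in remission counts as loss of response.
- **As a censoring date**, all later follow-up is discarded, and censoring may be informative when patients stop for toxicity.

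The rule would govern the separately reported MF/SS result. The PD-L1 groups, unless further split by diagnosis, and any overall curve would mix two definitions of DOR.

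A second defect sits in the same paragraph. Time to response and loss of response are defined by a 50% change in the global response score, but Appendix C gives that score only as CR, PR, SD, PD or Relapse. No percentage change can be computed from it.

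**Working it through.** The plan states no expected DOR, so there is no figure to reproduce. The check is calendar arithmetic: maximum DOR = off-treatment day minus day of first response.

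**Inputs**
- Last planned dose, cycle 6 day 22 (3.1): 5×28 + 22 = day 162.
- End of cycle 6 (3.2): 6×28 = day 168.
- Disease evaluation every 8 weeks, ±4 days, counted "from date of prior assessment" (3.6, footnote 4).
- Baseline timing (2.4): "The following should be performed within 28 days prior to the first dose of rhIL-15 unless otherwise noted". The calendar's baseline column shows 14 days.
- The plan does not define the off-treatment date, so both day 162 and day 168 are used.

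**Ceiling on the planned schedule**

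| Response first seen | Day | Maximum DOR (days) |
|---|---|---|
| First evaluation, 56 days from day 0 | 56 | 162−56 = 106 to 168−56 = 112 |
| Same, 4 days early | 52 | 110 to 116 |
| Same, 4 days late | 60 | 102 to 108 |
| First evaluation, baseline at day −14 | 42 | 120 to 126 |
| First evaluation, baseline at day −28 | 28 | 134 to 140 |
| Same, 4 days early | 24 | 138 to 144 |
| Second evaluation, from day 0 | 112 | 50 to 56 |
| Second evaluation, from day −28 | 84 | 78 to 84 |
| Third evaluation, from day 0 | 168 | −6 to 0 |
| Third evaluation, from day −28 | 140 | 22 to 28 |

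For a response at the first evaluation the ceiling is therefore 102 to 144 days (102/7 = 14.6 and 144/7 = 20.6 weeks).

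Outside the planned schedule:
- Minimum 26-day cycles put cycle 6 day 22 at 5×26 + 22 = day 152, giving 152−56 = 96 days.
- Five 7-day administrative delays raise 144 to 144 + 35 = 179 days. Toxicity holds lengthen it further. The cap moves but stays in place.

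**Follow-up left unused**
- Visits within 3 years under 3.5.3 number 3 + 8 + 1 = 12, or 3 + 6 + 2 = 11 if the 90-day phase ends at year 2.
- Under 6.3.6 a response from day 56 could be observed for 168 + 1,096 − 56 = 1,208 days (39.7 months). Under 6.3.3 it is 112 days (3.7 months).

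**Effect on the Kaplan-Meier median (illustration)**

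Assumptions: exponential DOR, 5 or 10 responders from day 56, off-treatment on day 168, 4,000 simulated trials. The true medians are assumed because the plan gives none.

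| Assumed true median (months) | Still in response at 112 days | Date as event: highest possible median (months) | Date as censoring: median not reached |
|---|---|---|---|
| 6 | 65% | 3.7 | 76–77% of runs |
| 10.1 | 78% | 3.7 | 92–95% |
| 12.6 | 82% | 3.7 | 96–98% |

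With follow-up to 39.7 months under 6.3.6, the median is reached in at least 99% of runs.

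**Loss-of-response threshold**

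Suppose the score is read as mSWAT, with baseline B = 100 and nadir N = 40.
- 6.3.3 read as nadir plus half the drop: 40 + 0.5×(100−40) = 70.
- Appendix C (skin), nadir plus half of baseline: 40 + 0.5×100 = 90.
- 6.3.3 read literally, half the difference: 0.5×(100−40) = 30, below the nadir. This happens whenever N exceeds B/3.

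The first two thresholds differ by 0.5×N, so they disagree whenever the nadir is above zero.

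**The case against.** **Disease-specific override.** Section 6.3.3 is the CTCL section and gives its own DOR definition, so it can be read as taking precedence over the general one. The plan does not say this. Even if it did, DOR would still stop at planned completion, event or censoring would still be undefined, and the scheduled follow-up would still go unused.

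**Early discontinuation only.** The sentence may have been aimed at patients who stop early. Its own wording covers any reason, section 3.8.1 counts completion as removal from therapy, and section 3.5 speaks of patients coming off treatment without progression. This reading fails.

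**Small stakes.** This is a Phase 1 trial with MTD and adverse events as primary endpoints, and no decision rests on DOR. Using the rates in section 1.2.5 (2 of 15 in CTCL, 38% in MF/SS), CTCL responders would number about 1 to 4 if 10 of 30 patients have CTCL, and about 4 to 11 if all do. This stands and limits the importance of the point. With so few responders, however, truncating each one matters more to the estimate.

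**Wording slip in the score.** Section 6.3.3 defines skin PR by mSWAT, so mSWAT was probably meant. That is plausible, but the threshold then still disagrees with Appendix C.

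**Incomplete post-treatment data.** Section 3.5.3 says patients may be assessed and allows a blood count or telephone contact as a fallback. Calendar footnote 16 limits dermatology assessment to selected patients. This stands as a caution about completeness. Censoring at the last disease assessment handles it, and it is no reason to discard the data that are collected.

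**Conclusion.** The plan is wrong as written and should be corrected before DOR is analysed. Followed literally, section 6.3.3 caps CTCL DOR at about 15 to 21 weeks for a response seen at the first evaluation, and at less for later responses. It can return zero or a negative value for a response first recorded at the third evaluation. These figures assume the planned 28-day cycles and an off-treatment date at last dose or end of cycle 6. Shorter cycles or delays move the first-evaluation ceiling to between 96 and 179 days, and holds can extend it beyond that.

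The conflict with section 6.3.6 concerns DOR. Time to progression is cut off by the same sentence but has no competing definition. It is not a listed endpoint, although section 10.4.3 mentions it in reporting. The MTD, response rate, PFS, EFS and OS are unaffected.

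**What to change.** - Delete the off-treatment sentence and the global-response-score formulas from section 6.3.3. Keep its skin-flare paragraph, so that an unconfirmed flare does not end DOR.
- Use one DOR definition in section 6.3.6 for all patients: from first CR or PR to first documented progression, loss of response or relapse, or death. For CTCL, these events are judged in any compartment under Appendix C. Otherwise censor at the last disease assessment, using the post-treatment assessments in section 3.5.3.
- State that for CTCL the Appendix C reference values (baseline or nadir) replace the smallest-measurement reference in section 6.3.6.
- Define CTCL time to response as the first date of global CR or PR under Appendix C.
- Keep time to progression as start of treatment to progression, without the off-treatment rule.
- If censoring at new anti-cancer therapy is wanted, write it into section 6.3.6 for all patients.

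The cost is protocol wording. Post-treatment imaging and the global score are already on the Study Calendar, so no new visits are needed.
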